### **Aims:**

#### Primary

1. To determine if long acting tolterodine confers more benefit than intra-vaginal low dose estrogen in the treatment of Overactive Bladder Syndrome at twelve weeks post treatment initiation.

#### Secondary

1. To determine if patients with subjectively unsatisfactory results with monotherapy (tolterodine or estrogen cream) receive further improvement in OAB symptoms with a change to combination therapy (tolterodine plus estrogen).
2. To compare symptom specific and general quality of life and patient satisfaction measures in women treated with oral anti-muscarinic therapy versus those treated with intra-vaginal estrogen versus those treated with both.
3. To describe any change in urinary frequency or leakage in the treatment groups on a 3-day bladder diary.
4. To describe any association of symptom improvement with changes in vaginal epithelial maturation assessment.
5. To compare voiding and post micturition symptoms including slow stream, hesitancy, straining, terminal dribble, and feeling of incomplete emptying in the treatment groups.
6. To correlate observed changes in symptoms of stress incontinence in the women in each treatment group.

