### **Research Design:**

The study design is a randomized controlled intent to treat trial where postmenopausal women seeking care for symptoms suggestive of OAB (urgency, frequency, urge incontinence, nocturia) would be randomized to treatment with Detrol LA in study arm #1, versus treatment with local estradiol vaginal cream (Estrace, *Warner Chilcott, Rockaway, NJ*) in study arm #2. After screening for inclusion and exclusion criteria (see list below) women would be randomly assigned to a treatment group. After 12 weeks of treatment the subjects who are not completely satisfied with the results of their current therapy will be offered the opportunity to add the other therapy to their treatment regimen (see study flow diagram below). All subjects will be followed for 52 weeks. In addition to being analyzed as part of their original randomized arm, patients who receive dual therapy will be sub-analyzed for further improvement in their OAB symptoms.

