## Study Flow Diagram

Baseline measurements will include lab findings (dip urinalysis, vaginal pH, vaginal maturation index), pelvic organ prolapse quantification evaluation, subjective assessment of vaginal atrophy, a post-void residual volume and a 3-day bladder diary. Women with an intact uterus will undergo a pelvic ultrasound to assess endometrial thickness at baseline and after 12 weeks treatment with estradiol. If they do not receive estradiol treatment no follow-up ultrasound will be performed. Questionnaires include the Overactive Bladder Questionnaire (OAB-q), Pelvic Floor Distress Inventory (PFDI-20), Pelvic Floor Impact Questionnaire (PFIQ-7), Pelvic Organ Prolapse/Urinary Incontinence Sexual Function Questionnaire (PISQ-12) and the SF-12, a short form general health inventory.

Detrol LA will be prescribed with a 4 mg dose QD. Estrace vaginal cream (0.1 mg estradiol per gram) will be prescribed as 0.5 grams (a finger tip length of cream) to be

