## Exclusion Criteria:

- Post void residual > 150 ml
- Glaucoma without ophthalmologist clearance
- HRT in the past 6 months
- Current anticholinergic treatment
- Breast cancer
- Impaired mental status
- Undiagnosed vaginal bleeding in past 12 months
- endometrial thickness on pelvic ultrasound > 5 mm
- History of thromboembolic event
- Gynecologic cancer
- Untreated urinary tract infection (would be eligible after treatment)
- Stage III pelvic organ prolapse or greater
- Recent diuretic medication changes (one month from change)
- Neurologic condition affecting bladder function (Multiple Sclerosis, Parkinsons, spinal cord injury, spina bifida)
- congestive heart failure
- prior pelvic irradiation
- interstitial cystitis

applied into the vagina nightly for six weeks, then twice per week for the duration of the study (12 months).

All subjects will be called at 4 weeks to monitor for side effects and for possible drug dosage adjustment. This will be accomplished using a standardized evaluation tool.

Subjects will then be seen at 12 weeks (primary outcome visit) where a physical examination will be performed and the indices collected at baseline as well as the study questionnaires and bladder diary will be repeated. Participants that are not completely satisfied with the outcome of their current treatment regimen will be offered the opportunity to add the other therapy to their regimen. This will be determined using the Patient Satisfaction Questionnaire (PSQ) and the Patient Global Impression of Improvement (PGII). Women who were administered estradiol and have an intact uterus will undergo a pelvic ultrasound to document no change in endometrial thickness after 12 weeks of therapy.

All patients will be seen at 24 weeks for an additional physical examination to repeat baseline indices, as well as the study questionnaires and the 3-day bladder diary. Women with an intact uterus who chose to add estradiol to their treatment regimen after the 12 week visit, will undergo a pelvic ultrasound to document no change in endometrial thickness after 12 weeks of estradiol therapy.

Finally, at 52 weeks, patients will be asked to complete an additional 3-day bladder diary, repeat the questionnaires and report their long-term management choice for treatment of their urinary symptoms via US mail.

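### Secondary aim 2 compares tolterodine, estrogen and both, but 'both' is reached only through incomplete satisfaction at week 12 plus choice, so that contrast is confounded by week-12 response

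*Combined protocol and SAP*

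**What the plan says.** - **Aims, Secondary, item 2** compares symptom-specific and general quality of life and patient satisfaction in "women treated with oral anti-muscarinic therapy versus those treated with intra-vaginal estrogen versus those treated with both". Item 1 asks separately whether women with unsatisfactory monotherapy results "receive further improvement in OAB symptoms with a change to combination therapy (tolterodine plus estrogen").
- **Research Design** randomises to two arms, tolterodine or estradiol cream. There is no randomised combination arm. Women who add the second drug stay in the analysis of the arm to which they were assigned ("In addition to being analyzed as part of their original randomized arm"). The section also plans a separate look at them: "patients who receive dual therapy will be sub-analyzed for further improvement in their OAB symptoms".
- **Methodology/Protocol, 12-week visit** (printed after the exclusion criteria): "Participants that are not completely satisfied with the outcome of their current treatment regimen will be offered the opportunity to add the other therapy". On how this is decided: "This will be determined using the Patient Satisfaction Questionnaire (PSQ) and the Patient Global Impression of Improvement (PGII").
- **Methodology/Protocol, 24-week visit:** women return "to repeat baseline indices, as well as the study questionnaires and the 3-day bladder diary". At week 52 the diary and questionnaires are repeated by mail.
- **Statistics** sizes the trial on the two-arm OAB-q comparison (SD 25, difference 20). For women who elect combination therapy it plans within-group nonparametric tests, because it expects few of them. It gives no between-group method for the contrast in aim 2.

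**The concern.** Membership of the third group is decided after randomisation, by an outcome (week-12 satisfaction) and then by choice. The monotherapy side is selected too: it keeps every satisfied woman and loses only dissatisfied ones. The difficulty is sharpest for satisfaction, which opens the gate to combination therapy and is also one of the outcomes compared.

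If the aim is followed as written, any effect of adding the second drug is mixed with the fact that those women were doing less well at week 12. With no add-on effect, combination users would tend to have worse later scores. If week-12 dissatisfaction is partly temporary, the same women could appear to improve more from week 12. Neither result measures the benefit of combination therapy, yet either could appear among the long-term findings that the Timeline plans to publish.

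**Working it through.** **1. The plan's own figure.** n per arm = 2(1.96 + 0.8416)² × 25² / 20² = 24.5, so 25, taking the test as two-sided (the sidedness is not stated). Adding 5 per arm gives 30 per arm and 60 in total. The figure reproduces, but it covers only the randomised two-arm comparison and supports no contrast with combination users.

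**2. Do the planned analyses repair the contrast?**

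| Planned analysis | What it gives | Combination vs monotherapy? |
|---|---|---|
| By original randomised arm | A valid comparison of two starting drugs, with optional add-on | No: it contains no combination group |
| Within-group tests in those who add | Before-after change, for aim 1 | No: it has no comparator |
| Aim 2 as worded | Three groups by treatment received | Yes, but selected on week-12 response |

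**3. Illustrative size.**

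From the documents: SD 25, the 20-point difference and 60 women.

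Assumed, because the documents do not say:
- SD 25 is the SD of scores at both visits (all results scale with it).
- There is no add-on effect, and all 60 women reach week 12.
- Latent week-12 satisfaction S is standard normal, and the lowest share *d* are not completely satisfied.
- A random share *u* of those women add the second drug.
- Satisfaction correlates *r* = 0.4 to 0.6 with a better week-12 score.
- Week-12 and week-24 scores correlate *c* = 0.5 to 0.7.
- The two starting arms are pooled.

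Formulas, with z = Φ⁻¹(d):
- Mean S of those who add = −φ(z)/d
- Mean S of the rest = [d(1−u)(−φ(z)/d) + φ(z)] / (1 − du)
- G = the difference between these two means
- Week-12 gap = 25·G·r, and week-24 gap = 25·G·q
- Apparent advantage on change from week 12 = 25·G·(r − q)
- Own before-after gain of those who add = 25·(φ(z)/d)·(r − q)

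Here q is the correlation of S with the week-24 score. It runs from rc (satisfaction matters only through the week-12 score, 'temporary') to r (equally related to both visits, 'stable').

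Worked case, d = 0.6 and u = 0.5 (18 of 60 women):
- φ(z) = 0.386; those who add −0.386/0.6 = −0.644; the rest (−0.193 + 0.386)/0.7 = 0.276; G = 0.920.
- Week-12 gap: 25 × 0.920 × 0.4 = 9.2, up to 25 × 0.920 × 0.6 = 13.8.
- Week-24 gap, temporary: 25 × 0.920 × 0.20 = 4.6, up to 25 × 0.920 × 0.42 = 9.7. Stable: 9.2 to 13.8.

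| d | u | Women adding, of 60 | G | Week-24 gap, temporary | Week-24 gap, stable |
|---|---|---|---|---|---|
| 0.9 | 0.25 | 13–14 | 0.25 | 1.3–2.6 | 2.5–3.8 |
| 0.8 | 0.25 | 12 | 0.44 | 2.2–4.6 | 4.4–6.6 |
| 0.6 | 0.50 | 18 | 0.92 | 4.6–9.7 | 9.2–13.8 |
| 0.7 | 1.00 | 42 | 1.66 | 8.3–17.4 | 16.6–24.8 |

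The gap is the number of points by which combination users look worse, with no true effect. The tabulated scenarios span about 1 to 25 points. Neither end is a bound: 90% dissatisfied with every one adding (54 of 60) would reach 29. A harsher model, in which the 30–70% with the worst week-12 scores elect, gives about 12 to 29 points for week-12-to-24 correlations of 0.3 to 0.7.

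**4. Change from week 12.** In the worked case, combination users look 2.8 to 6.9 points better on change if dissatisfaction is temporary, and no better if it is stable. For d from 0.4 to 0.9, their own spurious before-after gain runs from 0 (stable) to 7.2 points (temporary, d = 0.4).

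**The case against.** The strongest case on the other side is that this is a loosely worded secondary aim and not a planned confounded test.

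- **No formal three-way test is specified.** This stands. A reader might infer one from aim 2, but Statistics gives combination users only within-group tests, and Research Design keeps them in their original arm. The aim nevertheless says compare, whereas items 3 and 4 say describe, and nothing labels the contrast as non-randomised or adjusts for week-12 response.
- **Later satisfaction data may well be collected.** This stands. A reader might infer that the PSQ and PGII are not collected after week 12, because they are named only there and the listed questionnaires end with the "Sexual Function Questionnaire (PISQ-12) and the SF-12, a short form general health inventory". That is a baseline list, where satisfaction with study treatment would not be expected. The study flow diagram, which might show instruments by visit, is not visible in the text. The point cannot be settled either way.
- **The size rests on assumptions.** This stands. Statistics expects few women to cross over, and the low-uptake scenarios with 80–90% dissatisfied give only about 1 to 7 points. Non-random election could raise the gap.
- **Timing is partly implied.** This stands: the visits are fixed, and combination users cannot exist before week 12.
- **The original-arm analysis is already planned.** It is, and it is worth keeping, but it answers a different question from the contrast in aim 2.

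**Conclusion.** The point holds on the design alone and needs no figure: a contrast of combination with either monotherapy in aim 2 is confounded by week-12 response, and the analyses already planned do not repair it.

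Its size is unknown from the documents. On the stated assumptions the spurious week-24 OAB-q gap is about 1 to 25 points across the tabulated scenarios, against the protocol's 20-point benchmark. General quality of life and later satisfaction are not quantified. Combination users look worse at week 24 whenever week-12 satisfaction is positively related to later scores. That direction is built into the model and is not an independent finding. The opposite appearance on change from week 12 is possible but not assured.

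A reader might go further and doubt the trial's main result. The documents do not support that: the primary comparison is made at week 12, before any add-on, and both it and its sample size are untouched. The within-group tests for aim 1 can also stay, with a caution. This should be fixed, as a matter of wording and interpretation in a secondary aim.

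**What to change.** 1. **Reword aim 2** along these lines: *To compare symptom-specific and general quality of life between the two randomised arms at week 12, and at weeks 24 and 52 by original arm as treatment strategies (assigned starting drug, with the other drug added where a woman is not completely satisfied at week 12 and elects it). Satisfaction is compared between the randomised arms at week 12, and at later visits only if the PSQ and PGII are collected there.*
2. **Replace the third comparison group** with: *Any summary of women on both drugs beside those on monotherapy is non-randomised and exploratory. It is shown by starting arm with baseline, week-12 and later values. No superiority or inferiority of combination therapy is concluded from it.*
3. **Add beside the within-group tests in Statistics:** *These women were selected for incomplete satisfaction at week 12, so improvement from week 12 may partly reflect regression to the mean and is not by itself evidence of an add-on effect.*
4. **State whether** the questionnaires at weeks 24 and 52 include the PSQ and PGII.

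The cost is one reworded aim and a few sentences, with no extra patients or visits and no change to the add-on offer. Extra data are needed only if later satisfaction is to be compared and those instruments are not already collected then. The sponsor gives up an inferential claim about combination versus monotherapy that this design cannot support.

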### **Relevance:**

Lower urinary tract bladder storage symptoms include urinary frequency, urinary urgency, nocturia and urge incontinence. Overactive bladder syndrome is a condition in which urgency is the predominant symptom with or without urge incontinence and is usually accompanied by frequency and nocturia, as defined by the International Continence Society. These are distressing problems that have a major impact on quality of life. Prevalence of overactive bladder symptoms in women in the United States has been estimated to be 16-17%, and this prevalence increases with age.

The mainstay of treatment of women with OAB syndrome is pharmacotherapy with anticholinergic agents, as well as behavioral therapy. Anticholinergic agents are thought to exert their effect via antagonism of the muscarinic receptors of the detrusor muscle, thus blocking transmission of the parasympathetic nervous system with subsequent reduction in detrusor muscle contraction. This method of treatment has demonstrated a 60% response rate as reported in the Cochrane Database of Systemic Reviews. In addition to anticholinergic therapy, vaginal atrophy is often corrected as part of a pharmacologic treatment plan.

Vaginal atrophy is a condition that is vastly prevalent in post-menopausal women. It is thought to affect up to 48% of post-menopausal women. Many women with this condition experience vaginal dryness, irritation, dyspareunia, as well as urinary symptoms including

dysuria, urgency, frequency, nocturia, incontinence and recurrent urinary tract infections. Often these symptoms are dismissed as “nuisance” symptoms and treatment of atrophy is not initiated. With the waning levels of estrogen in the post-menopausal period the lower genital and urinary tracts experience thinning of the epithelium, loss of rugation, and reduced secretions. Atrophy results in elevated vaginal pH, changes in the usual urogenital flora, an increased risk of urinary tract infections, as well as loss of maturation of the vaginal epithelial cells.

Symptoms of urogenital atrophy may be improved with exogenous estrogen therapy. Mettler et al. demonstrated effective relief of post-menopausal atrophy symptoms using 25 micrograms of 17- $\beta$ -estradiol vaginally administered tablets twice per week. Endometrial evaluation pre and post treatment showed no neoplastic findings up to 2 years after induction of therapy.

Several studies have evaluated the role of estrogen in the treatment incontinence, as well as the treatment of OAB. The lower urinary tract shares common embryologic origin with the lower genital tract, and has been found to contain abundant estrogen receptors. Thus, hormonal treatment is expected to have an effect on urinary tissue, symptoms and function. Estrogen therapy has shown varying results on urinary symptoms, depending on the dose and route of administration of the estrogen as well as the type of pre-treatment symptoms.

Historical studies such as a 1941 study by Salmon et. al. showed improvement in urinary symptoms in 13 of 16 women who demonstrated vaginal atrophy and had lower urinary tract complaints that were treated with intra-muscular estradiol. These authors demonstrated that symptom improvement mirrored maturation of the vaginal epithelium induced by the estrogen therapy. In 1978, Walter et. al. showed a statistically significant decrease in frequency, urge, and urge urinary incontinence in a placebo controlled trial of 29 women treated with oral estradiol and estriol versus placebo. The finding of urge urinary incontinence resolved in 7 of 11 women in the active treatment group versus only 1 of 10 in the control group. Two years later, Samsioe et. al. showed that 3 mg of oral estriol produced substantial improvement in urge urinary incontinence in 34 women and was significantly better than placebo in a double blind cross-over designed study.

More recently, Cardozo et. al. demonstrated in a randomized controlled trial, using oral estriol given for 12 weeks, subjective and objective improvement in urgency and nocturia, but neither treatment group had statistical significance over placebo. Fantl et. al. in a randomized controlled trial failed to demonstrate an effect on either objective or subjective urinary outcomes in patients treated with 3 cycles of oral estrogen. In a descriptive study by the same author, less nocturia and a higher percentage of positive bulbocavernosus reflexes in women treated with estrogen supplementation was found, suggesting a lower sensory threshold in estrogen treated subjects. Rufford et. al. performed a placebo controlled trial of estradiol subcutaneous implants for treatment of the urge syndrome. Subjective urgency improved in both the active and placebo groups, whereas urge incontinence improved only in the active treatment group. Adverse events (vaginal bleeding) prohibited the authors from fulfilling their enrollment goals and thus possibly failing to see further differences in treatment groups.

More pertinent to our proposal are studies that employed local vaginal estrogen therapy for the treatment of lower urinary tract symptoms. Cardozo et. al. performed a double blind placebo controlled study of 110 women using vaginal estradiol tablets for the treatment of lower urinary tract symptoms. They found a statistically significant decrease in urinary urge in the active treatment group that had demonstrated pre-treatment sensory urgency. Lose et. al performed a 24 week study comparing the estriol vaginal ring versus the estriol pessary. With the primary outcome being subjective questionnaire data, they

demonstrated an approximate 50% reduction in bothersome lower urinary tract symptoms. This study was limited by lack of a placebo treatment arm.

In 2004, Cardozo et. al. performed a meta-analysis examining the effect of estrogen for the treatment of symptoms suggestive of overactive bladder. Local vaginal therapy was associated with a statistically significant improvement in frequency, nocturia, urgency, incontinence, bladder capacity, and first sensation to void. Zullo et. al demonstrated prevention of post-operative de-novo overactive bladder symptoms in women treated with vaginal estriol ovules after placement of a TVT suburethral sling for stress urinary incontinence. Women treated with post-operative vaginal estrogen therapy had a baseline urinary urgency rate of 7%; 6 months after surgery, the rate was 4%. Women not treated with post-operative vaginal estrogen therapy had a baseline rate of urinary urgency of 7%, and, 6 months after surgery, it increased to 29%.

The potential theories of why estrogen therapy may improve the symptoms of overactive bladder include increasing the sensory threshold of the bladder, increasing alpha-adrenergic receptor sensitivity in the urethral smooth muscle, promoting beta 3 adreno-receptor mediated relaxation of the detrusor muscle, and improving collagen quality and production in the peri-vesical and peri-urethral areas.

No studies have been conducted looking at the treatment of storage or overactive bladder symptoms using low dose local vaginal estrogen cream in comparison to anti-cholinergic therapy, and further, whether step-wise combination treatment confers superior symptom improvement than with anti-cholinergic or estrogen therapy alone. We also wish to compare the symptoms of stress incontinence and voiding dysfunction in these subjects.

[figure not shown]
### **Research Design:**

The study design is a randomized controlled intent to treat trial where postmenopausal women seeking care for symptoms suggestive of OAB (urgency, frequency, urge incontinence, nocturia) would be randomized to treatment with Detrol LA in study arm #1, versus treatment with local estradiol vaginal cream (Estrace, *Warner Chilcott, Rockaway, NJ*) in study arm #2. After screening for inclusion and exclusion criteria (see list below) women would be randomly assigned to a treatment group. After 12 weeks of treatment the subjects who are not completely satisfied with the results of their current therapy will be offered the opportunity to add the other therapy to their treatment regimen (see study flow diagram below). All subjects will be followed for 52 weeks. In addition to being analyzed as part of their original randomized arm, patients who receive dual therapy will be sub-analyzed for further improvement in their OAB symptoms.

